Appendix A: Schedule of Study Assessments

Appendix B: Patient-Reported Congestion Score

1.0 Background

Loop diuretic therapy is the cornerstone of heart failure (HF) symptom management. Symptoms of fluid retention and congestion are responsible for 90% of HF hospitalizations, and almost all (86%- 97%) patients hospitalized for HF receive intravenous (IV) loop diuretics.^{1,2-4} The incidence of diuretic resistance is unknown, given the lack of a consensus definition, but resistance is reported to occur in 25-35% of heart failure patients.⁵⁻⁷ Despite the prevalence of loop diuretic use in HF and frequency of diuretic resistance, guidelines by the Heart Failure Society of America (HFSA) and the American College of Cardiology Foundation/American Heart Association (ACCF/AHA) provide nonspecific guidance on diuretic regimen design in response to diuretic resistance. Both guidelines recommend (LOE IIA, Class B) the addition of a second type of diuretic (options listed include oral metolazone and intravenous chlorothiazide).^{8,9} As expected, 57% of physician questions about advanced HF management in a recent survey concerned diuretic titration.¹⁰

Addition of a second diuretic is a common practice to overcome diuretic resistance, despite the scarcity of literature to support this practice. A 2010 literature review of combining thiazide and loop diuretics found, “The aggregate body of literature is limited by the small size of studies, study design with lack of control groups, heterogeneous patient populations, wide variation in diuretic regimens, and focus on physiologic rather than clinical outcomes.”¹¹ In addition to lack of evidence guiding its use, combination diuretic therapy is further complicated by adverse events and costs associated with this practice. Electrolyte derangements are a common adverse effect of combination diuretic regimens, predisposing patients to cardiac arrhythmias.¹¹ Furthermore, each agent has its limitations: metolazone is subjected to erratic absorption due to its oral dosage form; whereas, intravenous chlorothiazide overcomes the absorption issue but is more costly.¹²⁻¹⁴ Clearly, a need to better understand the benefits and risk of these therapies exist.

A non-thiazide option, also mentioned in heart failure guidelines for fluid removal, is the oral vasopressin 2-receptor antagonist tolvaptan. This agent could be an equally effective alternative to thiazide diuretics with potentially less electrolyte derangement. In the EVEREST (Efficacy of Vasopressin Antagonism in Heart Failure Outcome Study With Tolvaptan) trials the addition of 30 mg tolvaptan daily was evaluated compared to IV loop diuretics in > 4,000 patients hospitalized for ADHF.¹⁵ Weight reduction was again seen as early as the 1st day, and weights at discharge or day 7 were 0.6 kg lower in trial A and 0.9 kg lower in trial B ($p < .001$). Most notably, no study reported hypokalemia with the combination of loop diuretics and tolvaptan.¹⁵⁻¹⁷ Another study demonstrated that 80mg furosemide plus 30mg of tolvaptan provided a reducing of 1.48kg (± 1.14 kg) at 48 hours in a small subset of an acute HF population.¹⁸ However this study was not conducted in patients who had developed diuretic resistance.

Given the importance of adequate decongestion in acute heart failure and the common occurrence of loop diuretic resistance, there is a critical need for evidence regarding the optimal selection of additional agents to restore diuretic efficacy.

2.0 Rationale and Specific Aims

Given the sparse amount of data regarding adjunctive diuretic strategies in acute heart failure, this study aims to address this gap by providing one of the first prospective trials comparing three different medications in addition to loop diuretics. By utilizing a prescriptive algorithm for loop diuretic dosing and other medical therapies that alter diuretic response, the study will address many of the limitations of previous studies such as the lack of a control group, retrospective design, and wide variations of both loop and thiazide diuretic regimens.^{13, 14} Metolazone will be

employed as the standard-of-care thiazide to mirror current clinical perceptions and to replicate a recent landmark diuretic study's thiazide use.^{11, 19-20} Our selected sample size will provide adequate power to detect clinically meaningful differences in outcomes, a further limitation of previous studies. The results of this study have the potential impact practice immediately as it will provide the first evidence to guide practitioners on the most appropriate next step to overcome diuretic resistance. The evidence from the results of this trial would have the potential to be included in future guidelines for heart failure management. Finally, this data could generate other hypotheses which would serve as the foundation of other studies.

Specific Aims

1. Compare the 48-hour weight change of either intravenous chlorothiazide or oral tolvaptan compared to standard-of-care oral metolazone when combined with standardized loop diuretic dosing for diuretic resistance in acute heart failure

Current heart failure guidelines recommend addition of a thiazide diuretic, listing either oral metolazone or intravenous chlorothiazide, to loop diuretic therapy as strategy to overcome loop diuretic resistance. At equipotent doses, these two therapies differ 250 fold in cost. To date, no prospective trial has compared the efficacy of these two commonly utilized therapies. We expect intravenous chlorothiazide will not provide an increase in clinically meaningful weight loss at 48 hours compared to oral metolazone.

Tolvaptan, an oral vasopressin 2 receptor antagonist, could restore diuretic efficacy when used in combination with loop diuretics. While the safety of this combination has been established in the EVEREST trials, tolvaptan has been formally studied in a limited capacity as combination therapy to restore loop diuretic resistance. From this sparse data, we expect oral tolvaptan will provide equal weight loss at 48 hours compared to metolazone.

2. Compare the adverse effects of electrolyte depletion and renal function changes between intravenous chlorothiazide or oral tolvaptan compared to standard-of-care oral metolazone when combined with standardized loop diuretic dosing for diuretic resistance in acute heart failure

Hypokalemia is a common adverse effect of combining a thiazide and loop diuretic, increasing the risk of atrial and ventricular arrhythmias in a population who is already at high risk. We expect intravenous chlorothiazide will require equivalent cumulative potassium repletion at 48 hours compared to oral metolazone. Hypokalemia has not been reported with the combination of tolvaptan and loop diuretics, likely due to tolvaptan's distinctive mechanism of action. We expect tolvaptan will require less cumulative potassium repletion at 48 hours compared to oral metolazone. This potential benefit could provide tolvaptan a unique advantage for combination diuretic therapy in environments when electrolyte monitoring cannot be routinely performed or in patients with frequent arrhythmic events.

3. Pharmacoeconomic analysis of the direct costs of intravenous chlorothiazide or oral tolvaptan compared to standard-of-care oral metolazone when combined with standardized loop diuretic dosing for diuretic resistance in acute heart failure

The average wholesale price for one dose of each agent according to Redbook online is \$1.50, \$357, and \$375 for metolazone 5mg tablet, chlorothiazide 500mg vial, and tolvaptan 30mg tablet respectively. We will perform a direct cost analysis including drug cost and other therapy-related costs. We expect both intravenous chlorothiazide and oral tolvaptan to have higher direct costs compared to metolazone. We expect the reduction in electrolyte repletion and accompanying adverse event treatment will reduce the cost difference of tolvaptan tablets compared to metolazone tablets.

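### Aim 1 expects near-null results on 48-hour weight loss, but section 9.3 gives only a test of difference and no pre-specified way to read a null result

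*Combined protocol and SAP*

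**What the plan says.** Aim 1 in section 2.0 is worded as a comparison: "Compare the 48-hour weight change of either intravenous chlorothiazide or oral tolvaptan compared to standard-of-care oral metolazone". Two predictions follow. For chlorothiazide: "We expect intravenous chlorothiazide will not provide an increase in clinically meaningful weight loss at 48 hours compared to oral metolazone". For tolvaptan: "we expect oral tolvaptan will provide equal weight loss at 48 hours compared to metolazone". Section 1.0 introduces tolvaptan in the same spirit: "This agent could be an equally effective alternative to thiazide diuretics with potentially less electrolyte derangement".

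Section 9.1 sets 60 patients, 20 per arm. Section 9.2 takes an SD of about 1.6 kg, calls 1.5 kg the minimum clinically meaningful difference, and gives 82.3% power to reject equal means at a type I error of 0.05. Section 9.3 compares each of the two arms with metolazone by Student's t test, two-tailed at 0.05, and summarises continuous data by arm as mean (SD) or median (IQR). It plans intention-to-treat and per-protocol analyses of the primary outcome.

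The document gives no confidence interval for a between-arm difference, no equivalence or non-inferiority margin, and no statement of how a non-significant result will be read. The 1.5 kg is used only for power.

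**The concern.** If either prediction is right, the t test will usually return p > 0.05. That is the outcome the sponsor expects, and it is the one for which the plan has no stated reading. A non-significant t test with 20 per arm is compatible with no difference and also with a difference that section 9.2 would call clinically meaningful. Only the interval tells the two apart.

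This matters because section 2.0 says of the study that "it will provide the first evidence to guide practitioners on the most appropriate next step to overcome diuretic resistance". That section words the effect on practice as a potential one, but the choice is between agents that it describes as differing 250-fold in cost (chlorothiazide and metolazone). Without a rule fixed in advance, a null result could be written up as equal efficacy without support, or a margin could be chosen after the data are seen.

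**Working it through.** **Inputs from the plan.** n = 20 per arm (9.1); SD 1.6 kg, difference 1.5 kg, two-sided alpha 0.05 (9.2, 9.3). Let D be mean weight loss in the test arm minus mean weight loss on metolazone, so that positive values are extra loss.

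**Step 1: the plan's own figure.** Standard error = 1.6 × √(2/20) = 0.506 kg, with 38 degrees of freedom. The noncentrality parameter is 1.5 / 0.506 = 2.96. Power from the noncentral t distribution is 82.36%, which reproduces the stated 82.3%.

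**Step 2: width of the interval.** Half-width of the 95% interval = t(0.975; 38) × SE = 2.024 × 0.506 = 1.02 kg. A result just short of significance has D of about 1.02 kg and an interval from about 0 to 2.05 kg, which contains 1.5 kg.

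**Step 3: how often p > 0.05 hides a real difference** (noncentral t).
- True difference 1.5 kg: 1 − 0.824 = 18% of trials.
- True difference 1.0 kg (assumed): 51% of trials.

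**Step 4: what the interval shows when the true difference is 0** (simulation, 2,000,000 trials, SD 1.6 kg). About 95% of trials are non-significant. Among these:
- the upper 95% limit reaches 1.5 kg in 16%;
- the 95% interval fails to exclude 1.5 kg in both directions in 32%.

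**Step 5: how the proposed readings would perform.**
- Chlorothiazide, upper 95% limit below 1.5 kg: met in 82% of trials at a true difference of 0 and in 2.5% at a true 1.5 kg. If the observed SD is 1.6 kg, it needs D below 1.5 − 1.02 = 0.48 kg.
- Tolvaptan, interval wholly within a symmetric range, true difference 0:

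| Range | 90% interval | 95% interval |
|---|---|---|
| ±1.5 kg | about 80% | 65% |
| ±1.0 kg (assumed) | about 24% | 6% |

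**Step 6: when significance and the 1.5 kg rule coincide.** For the one-sided chlorothiazide rule, this happens at any SD whenever chlorothiazide gives significantly less loss than metolazone. At SD 1.6 kg the overlap is 2.5% of trials at a true difference of 0 and 49% at a true −1.0 kg. A 95% interval that excludes 0 and also lies within ±1.5 kg needs a half-width below 0.75 kg, that is, an observed SD below 0.75 / (2.024 × √0.1) = 1.17 kg. That limit applies only to this two-sided case.

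**The case against.** The strongest reply is that aim and test agree. Aim 1 is to compare, 9.2 states a null of equal means, and 9.3 tests it. The expectations are predictions, not hypotheses to be proved. All of this stands. A reader might infer that this is a mislabelled equivalence trial with the wrong test or sample size, or that the sponsor intends to treat p > 0.05 as proof of equality. The documents support neither reading: power is stated correctly for a test of difference, and nowhere is a null result to be reported as equality.

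A second reply is that the missing piece is largely there already. Arm means, SDs and numbers determine the interval, and 9.2 names a clinically meaningful value. For chlorothiazide this is largely right: the prediction is itself worded in terms of clinical meaning, so only an explicit link to 1.5 kg is missing. For tolvaptan it is weaker. The prediction is equality, and 1.5 kg was chosen as a difference to detect, not as a margin within which two treatments count as equal. An interval can be derived afterwards, but a rule for reading it cannot.

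Third, the harm is a possible later misreading, not a planned one. That is fair, and it limits the weight of the point.

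**Conclusion.** This is a gap in interpretation that is cheap to close; it is not an error in the test, the power or the sample size. The plan predicts near-null results for both primary comparisons, and a p-value alone cannot support either. At the plan's own values, a non-significant result occurs in 18% of trials at a true 1.5 kg. Even with no true difference, 16% of non-significant trials leave a 1.5 kg gain open and 32% leave 1.5 kg open in at least one direction.

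The trial can usefully address the chlorothiazide prediction against 1.5 kg. For tolvaptan it could support a range of ±1.5 kg if that were justified in advance as a margin, but not one as tight as ±1.0 kg.

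The figures assume SD 1.6 kg, normal data, 20 evaluable patients per arm, and no multiplicity adjustment for the two comparisons (none is stated). The 1.0 kg values are assumptions. Fewer evaluable patients or a larger SD would widen the intervals.

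**What to change.** Add to section 9.3:

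1. Report each difference versus metolazone with its two-sided 95% confidence interval, on the same patients and values as the corresponding t test. State that p > 0.05 alone will not be reported as equal or equivalent.
2. Chlorothiazide: conclude that there is no clinically meaningful increase only if the upper 95% limit for extra weight loss is below the 1.5 kg of section 9.2. Otherwise, if the test is not significant, report the comparison as inconclusive.
3. Tolvaptan: say whether the 95% interval excludes 1.5 kg in each direction. Claim equality only if a margin, and the interval level that goes with it, are named and justified before the data are seen.
4. Precedence: a statistically significant difference in either direction is reported as a difference, with its size, even if the 1.5 kg rule is also met.

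The cost is wording only, with no added patients, data or procedures. The downside is that some null results will be reported as inconclusive, including the 16% of non-significant chlorothiazide results at a true difference of 0 shown above.

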3.0 Inclusion/Exclusion Criteria

Inclusion Criteria

Criteria for inclusion will be:

- Age of 18 years or older
- Hospital admission for hypervolemic decompensated heart failure complicated by loop diuretic resistance.
 - Hypervolemia will be diagnosed by the admitting provider as either (i) pulmonary artery catheterization with a pulmonary capillary wedge pressure greater than 19mmHg plus a systemic physical exam finding of hypervolemia (peripheral edema, ascites, or pulmonary edema on auscultation) or (ii) in the absence of pulmonary artery catheterization data 2 of the following signs or symptoms: peripheral edema ascites, jugular venous pressure > 10mmHg, or pulmonary edema on chest x-ray.
 - Loop diuretic resistance is defined as a provider decision to pursue combination diuretic therapy because of failure to reach provider defined adequate diuresis (can not exceed urine output of 2 L in past 12 hours) despite receipt of an intravenous loop diuretic dose of a furosemide equivalent of at least 240mg/day over at least the past 12 hours (40mg furosemide = 20mg torsemide = 1mg bumetanide).
- Standard-of-care monitoring, including 24 hour telemetry monitoring on an inpatient ward and a basic metabolic panel laboratory assessment twice daily during the study period.

Exclusion Criteria

Candidates will be excluded if they meet any of the following criteria at the time of enrollment:

- Decision to pursue hemodialysis by a nephrologist
- estimated glomerular filtration rate by the MDRD equation < 15ml/min/m²
- systolic blood pressure < 85mmHg
- pregnancy* or breastfeeding
- serum potassium < 3.0mEq/L
- serum sodium > 145mEq/L or < 130mEq/L
- severe malnutrition
- advanced liver disease
- inability to perform standing weights
- inability to collect and measure urine with either a foley catheter or urine collection containers
- concomitant therapy with strong CYP3A4 inhibitors/inducers (systemic ketoconazole, clarithromycin, itraconazole, telithromycin, saquinavir, nelfinavir, ritonavir, neofodone, rifampin, rifabutin, rifapentin, phenytoin, phenobarbital, carbamazepine, St. John's Wort), p-glycoprotein inhibitors (cyclosporine, erythromycin, tacrolimus, dronedarone, quinidine, or verapamil)
- non-study diuretics (spironolactone doses >75mg/day, eplerenone > 75mg/day, non-study thiazides or loop diuretics, or systemic acetazolamide, triamterene, or amiloride therapy)
- Thiazide medication administered in the previous 24 hours prior to randomization

*Pregnancy: In women of childbearing age who are not in menopause per patient report during screening, a serum pregnancy test will be ordered and negative prior to enrollment.

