5.3 Blinding

This study will be double blinded. Blinding will be performed by the enrolling site's investigational drug service pharmacy. A double-dummy strategy will prevent investigators from knowing the treatment arm during observation.

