5.4 Study Outcomes

The primary outcome will be 48-hour standing scale weight change (kg) from enrollment among the metolazone, intravenous chlorothiazide, and tolvaptan arms, using metolazone group as the comparator group for all other groups.

Secondary outcomes, using metolazone as the comparator group for each, will be:

- 48 hour net urine output (mls)
- mean change in serum creatinine, blood urea nitrogen, and eGFR at 24 hours, 48hours, and at hospital discharge
- mean change in diuretic efficiency at 24 and 48 hours from baseline value at enrollment
- mean change in serum potassium at 24 and 48 hours from baseline value at enrollment
- mean change in serum sodium at 24 hours, 48hrs, and at discharge from baseline value at enrollment
- cumulative dose of potassium (mEq) and magnesium (g) supplementation administered at 24 and 48 hours
- incidence of severe hypokalemia
- need for escalation in study-directed loop diuretic therapy at 24 and 48 hours
- addition of vasoactive or inotropic medication at 24 and 48 hours
- Treatment failure (definition below)
- Patient-scored congestion visual analog scale score at baseline, 24 and 48 hours (Appendix B)
- new cardiac arrhythmias (atrial and ventricular) during the study period
- receipt of inotropic therapy, dopamine, or nitroglycerin; requirement of ultrafiltration or hemodialysis during index hospitalization
- in-hospital mortality
- pharmacoeconomic analysis of the direct costs in each arm including the cost of:
 - study medication
 - additional non-trial protocol laboratory analysis cost related to monitoring of electrolytes
 - treatment of study medication related adverse effects (arrhythmias, hypotension, electrolyte repletion)
 - escalation of loop diuretic therapy doses
 - addition of additional therapies for suboptimal diuresis (inotropic therapy, vasodilators)
 - new initiation of renal replacement therapies (hemodialysis or ultrafiltration)
- Spot urinary electrolytes and diuretic urine concentration
- Pharmacokinetics and pharmacodynamics of the diuretics in the urine and blood
- Fractional excretion of sodium

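### The 24-hour pre-randomization washout covers thiazides but not tolvaptan, one of the three randomized drugs

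*Combined protocol and SAP*

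**What the plan says.** Section 3.0 applies its exclusion criteria at enrollment. Two of them concern other diuretics.

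- The washout item reads "Thiazide medication administered in the previous 24 hours prior to randomization".
- The concurrent-therapy item reads "non-study diuretics (spironolactone doses >75mg/day, eplerenone > 75mg/day, non-study thiazides or loop diuretics, or systemic acetazolamide, triamterene, or amiloride therapy". It states no look-back period and does not name tolvaptan.

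The inclusion criteria define loop diuretic resistance as "a provider decision to pursue combination diuretic therapy because of failure to reach provider defined adequate diuresis", on intravenous loop diuretic of at least 240 mg/day furosemide equivalent over at least 12 hours.

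Section 5.2 randomizes one third of patients to tolvaptan 30 mg once daily. Section 1.0 introduces tolvaptan as "A non-thiazide option, also mentioned in heart failure guidelines for fluid removal", so it falls outside the word thiazide in the washout item.

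Section 5.4 measures outcomes from the enrollment value: "The primary outcome will be 48-hour standing scale weight change (kg) from enrollment", and among the secondary outcomes "mean change in serum sodium at 24 hours, 48hrs, and at discharge from baseline value at enrollment". Section 5.5 counts sodium overcorrection from baseline, as a rise of at least 12 mEq/L in 24 hours or of more than 8 mEq/L in 12 hours.

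Neither the treatment-failure definition in 5.5 nor the rescue list under worsening heart failure in 7.2 names tolvaptan.

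**The concern.** The look-back serves to keep a randomized drug, or one of its class, from acting across the baseline. The plan does this for two of its three drugs. A tolvaptan dose given a few hours before enrollment passes the washout item because tolvaptan is not a thiazide. It can also pass the concurrent-therapy item, which looks only at enrollment. The inclusion wording makes such a patient less likely but sets no time limit on an earlier dose.

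For that patient, fluid lost and sodium gained before enrollment go uncounted, and any effect persisting afterwards is recorded under the assigned drug. If the assigned drug is tolvaptan, the patient has back-to-back exposure, and the overcorrection count starts from a sodium value that has already risen. Section 6.0 identifies overcorrection as the risk particular to the tolvaptan arm and cites the sodium floor of 130 mEq/L as one safeguard. That floor is also tested at enrollment. A patient lifted above it by open-label tolvaptan would qualify (an inference; the documents describe no such case).

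**Working it through.** **Which rule reaches a recent dose of each randomized drug (3.0)**

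| Drug | Recent dose, now stopped | Still being taken at enrollment |
|---|---|---|
| Metolazone, chlorothiazide | Excluded for 24 hours | Excluded (non-study thiazide) |
| Tolvaptan | No rule | Not named; excluded only if non-study diuretic is read broadly |

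The broad reading has some support, because 6.0 uses the term study diuretic when discussing tolvaptan. It does not fill the first column. The plan names non-study thiazides in the concurrent-therapy item and still adds a separate 24-hour thiazide washout, so the two items do different work.

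**The plan's own figure.** Inputs: 60 patients in three equal arms (9.1), so 20 per arm; SD 1.6 kg, difference 1.5 kg, alpha 0.05 (9.2); two-tailed t test (9.3). The standardized difference is 1.5/1.6 = 0.9375. Two-sample t-test power from the noncentral t distribution is 82.36%, against the stated 82.3%. The figure reproduces, and this point does not dispute it.

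**Size on the primary outcome, one patient at a time.** As an assumed shift per affected patient, take the 0.6 to 0.9 kg tolvaptan weight differences in 1.0. Those were measured at discharge or day 7, not 48 hours, and are not the residual effect of a stopped dose, so they serve only as a yardstick.

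- Standard error of a two-arm difference: 1.6 × √(2/20) = 0.506 kg.
- One patient's shift of an arm mean: 0.6/20 = 0.030 kg to 0.9/20 = 0.045 kg.
- As a share of the standard error: 0.030/0.506 = 5.9% to 0.045/0.506 = 8.9%.
- Excess of affected patients in one arm needed to move the difference by one standard error: 0.506/0.045 = 11.2, so 12; 0.506/0.030 = 16.9, so 17, out of 20.

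**Size as dilution.** Suppose a share f of patients is affected and each loses a share a of the 1.5 kg contrast, with the SD held at 1.6 kg. The effective difference is 1.5 × (1 − f × a). Both f and a are assumptions; the documents give neither.

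| f | Power, half the contrast lost (a = 0.5) | Power, all of it lost (a = 1) |
|---|---|---|
| 0 | 82.4% | 82.4% |
| 5% (3 of 60) | 80.4% | 78.4% |
| 10% (6 of 60) | 78.4% | 73.9% |
| 20% (12 of 60) | 73.9% | 63.7% |

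The last column is an extreme case.

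**Overcorrection count.** If open-label tolvaptan raised sodium by r mEq/L before enrollment, a counted rise of 12 mEq/L means a climb of 12 + r from the pre-drug value, over a correspondingly longer period. The rise is understated by r. The documents give no value for r.

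**The case against.** The case against has four parts.

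1. **The route in is narrow.** Entry follows failure of intravenous loop diuretic and a decision to start combination therapy, and a patient just given tolvaptan has in effect already had combination therapy. Section 6.0 says the added agent is commonly a thiazide, section 2.0 describes limited study of tolvaptan for this use, and it is priced there at $375 a dose. No passage suggests open-label use at the site. This stands, and it is why the likely number is put as small. It does not close the gap, since no rule bars the patient.

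2. **Randomization balances prior use.** A reader might infer that carry-over favours one arm. The documents do not support that: the exposure precedes allocation, so it is balanced in expectation and appears as noise or dilution. Nor is uncounted weight loss before enrollment a defect in itself, since the same holds for the loop diuretic every patient has received. This stands in full.

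3. **Rescue with open-label tolvaptan.** A reader might also infer that such rescue is never a treatment failure, so that the failure comparison depends on which drug the provider picks. That rests on a strictly literal reading. Section 5.5 speaks of additional non-study diuretic, which can reasonably cover open-label tolvaptan. The definition is the same in every arm, and rescue is chosen under blinding (5.3). Section 5.6 records non-study diuretics on Days 2 and 3, and Appendix A records cardiovascular medications at baseline, 24 and 48 hours. The 7.2 list lacks the general term but defines a safety-reporting category. No tolvaptan rescue rate is given. Only a wording clarification is warranted.

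4. **Missing figures.** Section 5.1 refers to a flow diagram that was not available, and a tolvaptan restriction could appear there. This cannot be ruled out.

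**Conclusion.** The point holds as a minor design improvement. Under 3.0 as written, a patient given open-label tolvaptan hours before enrollment is eligible, whereas one given a thiazide is not. The consequences are some noise or dilution in outcomes measured from enrollment, an understated sodium rise for the overcorrection rule, and possible back-to-back tolvaptan exposure. No material effect on the primary weight comparison is shown: at the assumed 0.6 to 0.9 kg, one patient is worth 6% to 9% of a standard error, and an imbalance of 12 to 17 patients would be needed to move the comparison by one standard error. The power losses in the dilution table depend wholly on assumed shares. The conclusion rests on the text available and assumes that the unseen flow diagram contains no tolvaptan restriction.

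**What to change.** In 3.0, reword the washout item so that the 24-hour look-back before randomization covers thiazides, tolvaptan and any other vasopressin antagonist. The sponsor may set a longer interval for the latter two; the documents give no duration of effect from which to choose one.

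As a clarification of wording only, add open-label tolvaptan to the treatment-failure list in 5.5 and to the rescue list under worsening heart failure in 7.2. If the flow diagram restates eligibility, align it.

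The cost is one short amendment and one added line on each of the screening and rescue forms. The downside is that a few recently treated candidates are lost or delayed.
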